- a. Screening Visit must be conducted in clinic for ALL De Novo group subjects. Subject eligibility will be assessed by the Investigator during screening and primary diagnosis will be verified by the ESC prior to Day 1 (for De Novo Group subjects only); subjects meeting OHSA#1 criterion on Day 1 and who otherwise meet eligibility criteria may be enrolled via RTSM.
- b. For 0169 Completers Group, Study 0169 procedures conducted at D29 will serve as the baseline assessments for D1 of Study 0170 .
- c. Follow-up visit is only applicable for those subjects that do not proceed to Study 0171 and will be completed two weeks from the date of the last dose. Those subjects proceeding to Study 0171 will enter from V9.
- d. The De Novo Group subjects would sign the consent before screening, thus screening visit is only applicable for De Novo Group subjects, and the 0169 Completers Group would sign the consent before V1 and would start with Day 1 of Study 0170.
- e. The assessments or procedures will be performed within 24-hours prior to subject taking the study medication (pre-dose). Following completion of study assessments, the subjects will take study medication on Day 2 in the morning.
- f. A complete medical and medication history evaluation will be performed during screening (for de novo subjects only).
- g. During the screening visit, subjects will receive thorough training on the OHQ disease instrument and will receive refresher training prior to completing the OHQ during each applicable study visit that occurs during treatment with study medication. Subjects should be rested prior to beginning the training.
- h. The tilt-table test should be performed following at least 12-hours of withdrawal from vasoactive medications. The tilt-table test should be performed at least 2 hours after meals and with an empty bladder.
- i. Subjects will be randomized via RTSM once they meet the randomization criteria
- j. The UPDRS scale should be completed in an ON state, and within 1-4 hours of taking the PD medications. All UPDRS Parts will be completed on Day 1 for De Novo Group subjects, while only Parts 2 and 3 of the questionnaire would be completed for 0169 Completers Group, and for subsequent visits for De Novo Group subjects.
- k. The assessment should be performed at approximately (± 2 hour) the same time of day on Day 1 (except Screening). Subjects should abstain from eating for at least 90mins prior to this assessment.

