criterion must be discontinued and undergo an end of study visit. The end of study visit must be completed within 2 weeks from the date of the last dose.

All subjects completing the initial 4-week OL treatment period and meeting the continuation criterion will continue receiving open label TD-9855 tablets for 12 additional weeks (16 weeks total).

Double-blind Period (Weeks 17 to 22)

Following the completion of a total of 16 weeks OL treatment with TD-9855 (V6) subjects will be assessed for randomization in a 1:1 manner. Eligible subjects will receive 6 weeks of double-blind treatment of TD-9855 or PBO once daily. Only subjects with OHS#1 score of ≤ 7 will be eligible for randomization for the double-blind treatment period.

Treatment period (Weeks 1 to 22):

No dose reduction is permitted during the treatment period.

Subjects unable to tolerate 10-mg TD-9855 will be discontinued from the study.

At any time during the study, if a subject meets at least one of the following stopping rules, they should be discontinued and undergo an end of study visit:

- A determination from the PI that further administration of the investigational product may pose a safety concern to the subject
- Sustained (at least 4 hours) SBP ≥ 180 mmHg or diastolic BP (DBP) ≥ 110 mmHg after 3 min of standing or after 5 mins in the sitting position, or a sustained (at least 4 hours) SBP ≥ 180 mmHg or DBP ≥ 110 mmHg measured in the supine state (head/torso elevated at approximately 30° from horizontal position).
- Intolerable AE, as determined by the PI
- Subject becomes pregnant

Safety assessments will include a physical examination, neurological examination, vital signs (body temperature, HR, respiratory rate [RR], and BP), body weight, 12-lead electrocardiograms (ECGs), laboratory tests (hematology, chemistry, and urinalysis), Columbia Suicide Severity Rating Scale (C-SSRS) and monitoring of AEs.

Safety will be periodically reviewed by an Independent Data Monitoring Committee (IDMC); see separate charter.

Subjects will be requested to refrain from making any significant dietary changes throughout the duration of the study. During their scheduled visits, subjects should be reminded to maintain an adequate fluid intake.

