Subjects completing the 6-week double-blind treatment period will be eligible to continue into the OL, long term safety study (Study 0171). Those subjects who do not complete the 6-week double-blind treatment period or who choose not to continue into Study 0171 will complete the Early Termination Visit (V9) or Follow-up visit (V10), respectively. The Follow-Up Visit must be completed 2 weeks from the date of the last dose.

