6.3.10. Treatment Day 155 – Visit 9/ Early Termination

Subjects completing Day 155 (V9) can proceed to Study 0171 following this visit. The following procedures will be performed on the Day 155 visit (+/- 3 days) after the daily dose of TD-9855/Early Termination:

The following procedures must be completed first, and in the order below:

- Review concomitant medications and smoking usage
- OHQ subject training
- OHQ (OHSA and OHDAS)
- PGI-S
- C-SSRS

The following procedures are listed in the recommended order, however flexibility for scheduling is permitted:

- NMSS
- HADS
- UPDRS (only for patients with PD)
- PDQ-8 (only for patients with PD)
- UMSARS (only for patients with MSA)
- COMPASS-31 (only for patients with MSA)
- EQ-5D-5L
- BSFC-s
- Orthostatic standing test
- Vital signs: HR, SBP, and DBP; RR and body temperature
- Weight (kg)
- Physical examination
- Neurological examination
- 12-lead ECG (in triplicate separated by at least 1 minute for each replicate, after the subject has been resting for at least 5 minutes)
- Pregnancy test (in women of childbearing potential only)
- Blood collection
 - Hematology
 - Chemistry
- Urine collection
 - Urinalysis
- Wearable device collection
- Incidence of falls – subject diary review for completion
- Dosing and Rescue medication diary review for completion
- AE assessment (AEs, SAEs, AESIs)
- Collect and review study medication

6.3.11. Follow-up Day 169 – Visit 10

The follow-up visit is applicable only for those subjects that will not proceed to Study 0171 and will be completed two weeks from the date of the last dose.

The following procedures will be performed on the Day 169 visit (+/- 3 days):

- Review concomitant medications and smoking usage
- C-SSRS

- Vital signs: HR, SBP, and DBP; RR and body temperature
- Weight (kg)
- AE assessment (AEs, SAEs, AESIs)

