7.4.2. Adverse Event and Serious Adverse Event Recording

All AEs, regardless of seriousness, severity, or causal relationship to study medication, will be recorded from signing informed consent through the last study visit (or last subject contact in the case of a follow-up telephone call). The AEs will be recorded on the AE page of the CRF. The SAEs, regardless of relationship to study medication will be recorded from signing informed consent through the last study visit (or last subject contact in the case of a follow-up telephone call). ****Exception for Subjects entering from Study 0169 (0169 Completers Group):*** Adverse Events, including Serious Adverse Events, that start after the Study 0170 ICF is signed, but before the first dose on Study 0170 is taken, are considered events originating in Study 0169. Additionally, Investigators may report SAEs assessed as related to study medication through 30 days following the last study visit (or last subject contact in the case of a follow-up telephone call). All SAEs will be recorded on both the SAE/AESI Report Form and the AE page of the CRF and should include the following:

Description of event:

- Signs and symptoms due to a common etiology should be reported as a single diagnosis; for example, cough, runny nose, sneezing, sore throat, and head congestion would be reported as “upper respiratory infection.”
- A diagnosis or description must be as specific and as complete as possible (e.g., “lower extremity edema” instead of “edema”).
- Hospitalization or surgical procedures should not be used as AE terms (e.g., if a subject was hospitalized for cholecystectomy due to cholecystitis, the AE term should be recorded as cholecystitis, and not as the procedure, cholecystectomy).
- “Death” should not be used as an AE term unless the cause of death is unknown. For events with a fatal outcome, the cause of death should be the AE term (e.g., if a subject died of an acute myocardial infarction, the AE term should be recorded as “Myocardial Infarction” and the event outcome as fatal).

Relationship to study medication: The Investigator will make an assessment of the causal relationship of the study medication to the AE using the guidelines in Section 7.3.2.

Severity: The severity of the AE will be assessed using the guidelines in Section 7.3.1.

Outcome: The outcome of AEs will be recorded.

Therapeutic measures: Measures taken for the treatment or management of the AEs will be recorded.

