8.6.2. Adverse Event Data

The AEs will be coded to the preferred terms (PTs) of the Medical Dictionary for Regulatory Activities (MedDRA[®]). Summaries will be presented by system organ class (SOC), PT, and severity (mild, moderate, severe), along with the number and percentage of subjects for whom events were reported.

For subjects continuing from OL phase to the double-blinded randomized withdrawal phase, an AE that begins on or after the date of the first dose of TD-9855 up to the date of last dose of TD-9855 in OL phase will be considered TEAE for OL phase. For subjects discontinuing the study during the OL phase, an AE that begins on or after the date of the first dose of TD-9855 and up to the date of last dose of TD-9855 plus 14 days follow-up period will be considered TEAE for OL phase.

In the double-blinded randomized withdrawal phase, a TEAE is defined as any AE that begins on or after the date of the first dose of study medication post randomization and up to the date of last dose of study medication plus 14 days follow-up period.

The number and percentage of subjects who experience TEAEs will be summarized. Summaries of TEAEs will include the following:

- All AEs, by SOC and PT and also by PT (by descending overall frequency)
- All AEs, by SOC, PT, and severity
- All study medication-related AEs, by SOC and PT
- All study medication-related AEs, by SOC, PT, and severity

- All AEs leading to premature discontinuation of study medication, by SOC and PT
- All AEs leading to temporary interruption of study medication, by SOC and PT
- All SAEs, by SOC and PT
- All study medication-related SAEs, by SOC and PT

All AEs reported will be listed by subject. A separate listing will be provided for all subjects who experience an SAE. Separate listings will also be provided for subjects who discontinued study treatment prematurely because of AEs and subjects who temporarily interrupted study treatment because of AEs. The AESIs, as described in Section 7.1.4, will be listed and summarized.

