Safety assessments will include a physical examination, neurological examination, vital signs (body temperature, HR, respiratory rate [RR], and BP), body weight, 12-lead electrocardiograms (ECGs), laboratory tests (hematology, chemistry, and urinalysis), Columbia Suicide Severity Rating Scale (C-SSRS), and monitoring of AEs.

Subjects completing the 6-week double-blind treatment period will be eligible to continue into the open-label, long-term safety study (Study 0171). Those subjects who do not complete the 6-week double-blind treatment period or who choose not to continue into Study 0171 will complete the Early Termination Visit (V9) or follow-up visit (V10), respectively. The Early Termination Visit or Follow-Up Visit must be completed 2 weeks from the date of the last dose.

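### Follow-up rules for subjects who stop early conflict, so collection of new adverse events can end before the 14-day TEAE window closes

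*Protocol*

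**What the plan says.** The documents describe follow-up after the last dose in several ways.

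- **Double-blind period, Protocol 3.1 (and synopsis).** Double-blind non-completers and completers who decline Study 0171 "will complete the Early Termination Visit (V9) or Follow-up visit (V10), respectively". Timing is attached to V10 only: "The Follow-Up Visit must be completed 2 weeks from the date of the last dose".
- **Week 4 non-continuers, Protocol 3.1 (and synopsis).** "The end of study visit must be completed within 2 weeks from the date of the last dose".
- **Stopping-rule subjects, Protocol 3.1 (and synopsis).** An end of study visit, with no timing.
- **Table 1, footnote c.** "Follow-up visit is only applicable for those subjects that do not proceed to Study 0171". Protocol 6.3.11 repeats it: "The follow-up visit is applicable only for those subjects that will not proceed to Study 0171". The description of study periods in Protocol 3.1 and SAP 4.1 likewise gives a two-week follow-up to those not entering Study 0171.
- **SAP 4.1.** "The Early Termination Visit or Follow-Up Visit must be completed 2 weeks from the date of the last dose".
- **SAP 9.5.** Mentions in passing a follow-up visit at 10 days.

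On collection, Protocol 7.4.2 says AEs "will be recorded from signing informed consent through the last study visit", or through the last contact where that is a telephone call. Protocol 6.4.10.2 and SAP 9.1 put the end of collection at the end of follow-up.

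On counting, Protocol 8.6.2 says that for an open-label discontinuer an event starting after first dose and "up to the date of last dose of TD-9855 plus 14 days follow-up period will be considered TEAE for OL phase". It uses the same 14 days after last dose for the randomized withdrawal phase, and so does SAP 9.1.

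**The concern.** The TEAE definition assumes that someone is still asking about new events 14 days after the last dose. The visit rules guarantee this for completers who attend V10 at two weeks, but not for early stoppers. Two sites can follow different sections, both comply, and observe similar subjects for very different times off drug.

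The group includes subjects stopped for sustained high blood pressure or an intolerable AE. Protocol 1.4 lists syncope and increases in heart rate and blood pressure as important potential risks, so the days after stopping carry safety information. If new events in that interval are not collected, the TEAE numerator is too low for these subjects. In the double-blind phase the shortfall could differ by arm if early stopping does.

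**Working it through.** **1. The plan's own figure.** Table 1 puts V9/ET at Day 155 and V10 at Day 169. 169 − 155 = 14 days, which agrees with the two-week follow-up and the 14-day TEAE window. The schedule therefore covers the window when V10 takes place on its nominal day, or when an ET visit is timed at two weeks.

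**2. Which rule applies to an early stopper?** Under Protocol 3.1 only subjects who complete the double-blind period may enter Study 0171. Every early stopper is therefore someone not entering Study 0171.

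- Footnote c and 6.3.11, read literally, give that subject V10 at two weeks.
- The double-blind text of 3.1 gives a double-blind early stopper V9/ET, untimed, and assigns V10 to the other group.
- SAP 4.1 moves the ET visit to two weeks.
- The open-label text of 3.1 gives Week 4 non-continuers a visit at any time from day 0 to day 14, and stopping-rule subjects a visit with no stated time.

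No section says which text prevails. One visit on exactly day 14 would satisfy both the Week 4 rule and SAP 4.1. The defect is that nothing requires a visit that late.

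**3. Unobserved part of the window.** Let d be the days from last dose to last visit, with no later contact. Unobserved days = 14 − d. Fraction of drug remaining = 0.5^(24d / half-life), using the stated half-life of 30 to 40 hours (Protocol 1.3.1). The values of d are illustrative, because the documents give no minimum.

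| Last visit, day d | Unobserved days of 14 | Half-lives elapsed | Drug remaining |
|---|---|---|---|
| 1 | 13 | 0.6 to 0.8 | 57% to 66% |
| 3 | 11 | 1.8 to 2.4 | 19% to 29% |
| 7 | 7 | 4.2 to 5.6 | 2% to 5% |
| 14 | 0 | 8.4 to 11.2 | 0.3% or less |

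The last two columns apply only to subjects whose last dose was active. Placebo subjects took their last active dose before the randomized treatment began.

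**4. Effect of the V10 window.** V10 is allowed ±3 days. 14 − 3 = 11, so even a V10 within its window can leave 3 of the 14 days unobserved.

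**5. Size of the group.** Planned enrolment is 258 and planned randomization 154; 258 − 154 = 104 not randomized. This includes subjects who finish 16 weeks and then fail the randomization criteria, so it is an upper bound for open-label early stoppers. The documents give no number for double-blind dropouts, nor for subjects with an early last visit.

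**The case against.** The strongest reply is that most of the text points one way. The period description, footnote c and 6.3.11 give a two-week follow-up to anyone not entering Study 0171, and 8.6.2 itself speaks of a 14-day follow-up period for open-label discontinuers. An ET visit followed by V10 fits all of these. Collection is also wider than the last visit: 7.4.2 extends to a last telephone contact, 6.4.10.2 and SAP 9.1 refer to the end of follow-up, 7.4.2 allows related SAEs to be reported for 30 days after the last visit, 6.8.2 encourages continued safety assessments after an adverse reaction, and 7.5 follows events already under way.

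This reduces the gap but does not close it. The end of follow-up is undefined for a subject whose last visit is an ET or end of study visit. The 30-day provision is optional and limited to related SAEs, 6.8.2 encourages without requiring, and 7.5 does not reach new events. No passage requires new AEs to be sought up to day 14 in an early stopper.

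A reader might infer more than the documents support:

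- **That each subject is credited with 14 days of observation.** The window only classifies events that were recorded. Exposure in SAP 9.2 is last dose minus first dose plus 1, so no off-drug person-time is added.
- **That the two-week maximum governs subjects stopped for safety.** It is attached to Week 4 non-continuers; the stopping-rule visit is simply untimed.
- **That nothing is assessed at the time of stopping.** This would follow only if SAP 4.1 governed visits, but that section calls itself a summary and refers to the protocol.
- **That 40% of subjects lose follow-up.** The 104 is everyone planned not to be randomized, not a count of those affected.

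**Conclusion.** The inconsistency is real and should be corrected. A site that follows the early-stopper text of Protocol 3.1 can end collection of new AEs anywhere from the day of last dose onward, leaving up to 14 days of the TEAE window unobserved, and 13 after a day-1 visit. The likely effect is under-counting of late off-drug events among early stoppers. Whether it differs by arm depends on how early stopping differs by arm, which cannot be known from the plan.

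The conclusion assumes that a site may comply with any one of the conflicting passages, and that it makes no contact beyond those required. How many subjects are affected is not stated. The sample size calculation does not depend on this point.

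**What to change.** The sponsor should reconcile these places into one follow-up rule: Protocol 3.1 (period description, Week 4 non-continuers, stopping rules, double-blind non-completers) with the matching synopsis text, Table 1 footnote c, 6.3.11, 6.4.10.2, 7.4.2, SAP 4.1 and the 10-day visit in SAP 9.5. Which visit schedule is right is for the sponsor to settle.

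For data collection, the end of AE recording in 7.4.2 and 6.4.10.2 should be aligned with last dose plus 14 days, the window both documents already use, for every subject not entering Study 0171, including open-label discontinuers. That needs a contact on or after day 14, because V10 within its window can fall on day 11. A telephone call is enough for AEs, and 7.4.2 already contemplates one; it does not replace the vital signs and weight taken at V10.

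Parts of the SAP are in the past tense, so conduct may already be complete. In that case, report the actual days observed after last dose, by arm for the double-blind phase and separately for open-label discontinuers, so that readers can judge how far the TEAE window was covered.

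The cost is wording in both documents and one further contact for some early stoppers.

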3.2. Rationale for Study Design

Utilizing a randomized withdrawal following a predefined open label period, this study is designed to evaluate worsening from baseline in the OHSA#1 score of 1.0 point and a worsening of disease severity as assessed by a 1-point change in Patient Global Impression of Severity (PGI-S), in subjects with symptomatic nOH with a primary diagnosis of MSA, PD, or PAF following 6 weeks of daily treatment with TD-9855 at a dose of 10-mg compared to placebo. OHSA#1 is the validated primary efficacy endpoint in this patient population. The inclusion of PGI-S with OHSA#1 further exemplifies the patient-centric assessments thereby refining the treatment failure criteria. Prior to the randomized withdrawal phase of the study, all eligible subjects will receive OL TD-9855 for a period of 16 weeks. The OL period is designed to capture durability of effect following long-term TD-9855 administration. This durability of effect is confirmed through the subsequent randomized withdrawal period. The eligibility criteria are designed to adequately characterize these subjects and will include confirmation from an ESC (committee of independent neurologists) to determine the appropriateness of each subject for study inclusion. Prespecified population and PK and pharmacodynamic sampling will be used to further profile TD-9855 and the relationship between plasma exposure and TD-9855 efficacy. A dedicated charter outlining the procedure will include the details needed on the ESC form, a timeline for review, and the decision conveyed. In addition, an IDMC comprised of independent key opinion leaders, potentially from the field of neurology, cardiology, dysautonomia, and biostatistics, will evaluate the safety of TD-9855, with a dedicated charter outlining Study 0170 assessments at planned time points. Prespecified safety endpoints and measurements have been selected based upon their known relevance to a patient population that has been diagnosed with MSA, PD or PAF. Subjects that complete Study 0170 will be eligible to participate in Study 0171, which is designed to evaluate the long-term safety of TD-9855 in a 6-month OL design.

3.3. Selection of Dose and Duration of Treatment

TD-9855 has been previously investigated in FM and ADHD at doses up to 20 mg QD. TD-9855 was also investigated in a study in patients with nOH. Study 0145 was conducted in three parts including Part A (exploratory), Part B (proof-of-concept), and Part C (ongoing OL extension) to determine if TD-9855 improves the acute pressor response and OHSA#1, respectively. OHSA#1 is a measure of dizziness, lightheadedness, feeling faint, or the sensation of being about to black out.

Part A evaluated the dose response of single, ascending doses up to 20 mg. Although no dose response was observed, a numerical trend in increased seated and standing SBP was observed at the higher doses. An improvement in standing time of approximately 100 seconds was observed at 4 hours after dosing at 10 mg.

In Part B, subjects treated with TD-9855 (single dose up to 15 mg) demonstrated a sustained increase of approximately 20 mmHg in SBP over baseline following 3 minutes of standing at 4, 7, and 9 hours post-dose. No such increase in SBP was observed in placebo-treated subjects.

Part C evaluated durability of response, safety, and tolerability of TD-9855 over 20 weeks in an open label extension design. Top line results of interim data available for the first 4 weeks of the study (through Day 29) demonstrate durable improvements in subjects' disease symptom severity after treatment with TD-9855, as measured by OHSA #1.

Subjects demonstrated a mean symptom improvement of 2.4 points from baseline at four weeks. Importantly, mean symptom improvement from baseline was greatest (3.8 points) in nOH subjects who reported dizziness symptoms (OHSA#1 \geq 4) at baseline. Additionally, TD-9855 consistently increased systolic blood pressure (SBP), including clinically meaningful increases in standing SBP at the 3-minute assessment at all time points up to Day 29. There were no drug-related SAEs reported, and TD-9855 was generally well tolerated in the study. Per interim data from the first 4 weeks of Part C of Study 0145, the majority of subjects received TD-9855 10-mg QD.

Based on the results of the human positron-emission tomography study in healthy volunteers, the estimated IC₅₀ of TD-9855 for NET inhibition is 1.21 ng/mL. Accordingly, based on the population PK-pharmacodynamic model for TD-9855 in healthy and diseased subjects, 10-mg dose of TD-9855 is expected to achieve >80% NET inhibition in a majority of subjects. Thus, 10-mg dose of TD-9855 is considered adequate to achieve the desired pharmacological and clinical effect while minimizing the risk for safety concerns in subjects with symptomatic nOH.

